**MELVIN AND BREN SIMON
CANCER CENTER**

INDIANA UNIVERSITY

**The Role of ^{68}Ga -PSMA-11 PET in Surgery Guidance in Prostate
Cancer: A prospective Pilot trial**

INDIANA UNIVERSITY PROTOCOL

IUSCCC-0760, IRB#11330

**Principal
Investigator:** [name], MS
Assistant Professor of Urology
Indiana University School of Medicine
[name]
[name]
[contact]
Office: [contact]
[contact]
[contact]

Co-investigators: [name]
Professor of Urology
[contact]

[name]
Professor of Radiology
[contact]

[name]
Professor of Radiology
[contact]

[name]
Professor of Radiology, Vice Chair of Research
[contact]

[name]
Virgil H. Moon Professor of Pathology, Department of Pathology
and Laboratory Medicine
[contact]; [contact]

[name]
Assistant Professor of Radiology
[contact]

[name]
Assistant Professor of Clinical Radiology
[contact]

[name]
Associate Professor, Director of Diagnostic Physics, Dept.
of Radiology
[contact]

[name]
Professor of Biostatistics
[contact]

[name], MS
Biostatistician, Department of Biostatistics
[contact]

Support: Indiana University Departments of Urology, Radiology, and Pathology

American Cancer Society
Institutional Research Grant # 19-144-34-IRG (\$40,000)

IND#: 141706

Date of Protocol: March 29, 2022

INVESTIGATOR'S AGREEMENT

By signing below, I confirm that I have read this protocol and agree:

- To assume responsibility for the proper conduct of this study at this site
- To conduct the study according to the procedures described in this protocol and any future amendments
- Not to implement any deviation from, or changes to, the protocol without written approval from the Institutional Review Board (IRB), except where necessary to eliminate immediate hazard to the subject(s)
- That I am aware of all updates and will comply with all applicable regulations and guidelines

Principal investigator's signature

Date

[name], MS

Principal investigator's name (print)

Assistant Professor of Urology,
Indiana University School of Medicine

Principal investigator's title (print)

PROTOCOL SYNOPSIS

Study Design:	Prospective, pilot phase 2 clinical trial, single arm (non-randomized)	
Test Factor/Exposure:	PSMA PET-CT: ^{68}Ga -PSMA-11 PET-CT with Siemens Biograph Vision scanner or similar PET-CT to guide surgical planning. This will be compared to the standard of care MRI.	
Duration of Treatment:	Patients will undergo injection of ^{68}Ga -PSMA-11 PET-CT prior to definitive surgery. Quality-of-life will be tracked through 12-months follow-up.	
Enrollment:	n=55	
Primary Objective and Endpoint:	
Objective: Obtain PSMA-PET imaging preoperatively and calculate performance for predicting extra-prostatic extension based on whole-mount pathology (gold standard).
	
Endpoint: Sensitivity and Specificity for detecting extra-prostatic extension of cancer at the nerve bundles

Secondary Objectives and endpoints	
Objectives:
 
 1) Quantify the frequency of proper treatment changes directed by PSMA-PET, focusing on appropriate preservation of surrounding structures important for genito-urinary function including: 1) Bladder neck, 2) Nerve bundles, 3) Urethral Sphincter (Figure 4). 	
Endpoints:
 
 1) Rate of treatment changes and rate of treatment changes that were appropriate based on pathology.
Exploratory	
 2) Directly compare PSMA-PET performance for predicting extra-prostatic extension to standard-of-care assessments. 	
 2) Sensitivity/ Specificity/ PPV/ NPV for PSMA-PET vs. MRI vs. ultrasound-based nomogram.

	
3) Assess quality of life changes from preoperative baseline.
 
4) To assess whether kinetic modeling tools are useful for improving detection of the location and extent of tumor in ^{68}Ga-PSMA-11 PET/CT images (going beyond the standard PET map of regional radiotracer concentrations, additionally examining differences in regional pharmacokinetics to possibly further differentiate benign and neoplastic tissue).
	
3) Quality-of-life: IIEF-15 (Erectile function score), EPIC-26 (Pad use), SF-36 (overall mental and physical health domains).
 
4) Qualitative and quantitative changes in PET image appearance after voxel-by-voxel application of kinetic modeling tools to define regional pharmacokinetics (compared to standard PET reconstructions showing simply the integrated concentration of regional radioactivity over the imaging period).

Inclusion Criteria:		
 1. Men diagnosed with clinically significant prostate cancer who are scheduled or scheduling for prostatectomy 2. Prostate pathology results consistent with: 
 a. Gleason 3+4 \geq 1 core with pattern 4 \geq 20% or b. \geq 3 cores of Gleason 3+4 or c. NCCN unfavorable intermediate risk or d. NCCN high-risk or e. NCCN very-high risk 3. Scheduled for standard of care MRI or has recently completed standard of care MRI (within 6 months). Willing and able to lie still for approximately 50 minutes in an enclosed space for the PET/CT and MRI
Exclusion Criteria:		
 1. Participation in another investigational trial involving research exposure to ionizing radiation concurrently or within 30 days. 2. Does not meet safety criteria for MRI scan (e.g. metal implant that could affect prostate imaging). 3. Significant acute or chronic medical, neurologic, or illness in the subject that, in the judgment of the Principal Investigator, could compromise subject safety, limit the ability to complete the study, and/or compromise the objectives of the study.

[figure not shown]
Number of Sites:	Indiana University Simon Cancer Center, IU Health University Hospital, IU Health North, IU Health North medical office building, IU Health Schwarz Cancer Center, IU Health Methodist Hospital, IU Health Neuroscience Center/Goodman Hall
-------------------------	--

2 SCHEMA

3 BACKGROUND

3.1 Background & Preliminary Work

Metastatic prostate cancer rates have dropped significantly over the past 30-years, due to early aggressive prostatectomy and radiation therapy. However, hundreds of thousands of survivors have significant treatment-related side-effects, including urinary incontinence and erectile dysfunction. Treatment related side-effects result from collateral damage to structures alongside the prostate, such as nerves (erections) and sphincter muscle (incontinence). Injury or wide resection of sphincter and nerves is frequently intentional, or planned, to ensure all cancer is removed; yet, in hindsight it often appears this wide resection was not required. That is, a high percentage of the time the cancer is not extending outside the prostate as suspected or feared from biopsy and imaging-based staging. Prostate cancer is unique — most cases of extra-prostatic extension (extension into muscle and nerves) is not visible either on standard preoperative imaging, or to the operating surgeon during resection. Extra-prostatic extension is instead discovered on pathologic analysis *after* the patient has left the operating room. Prostate cancer has other unique features that make operative planning difficult: (1) it is multi-focal in up to 80% of subjects (Fig. 1); (2) it often presents with mixed grade lesions (Fig. 1); and (3) conventional imaging modalities (ultrasound, MRI) can miss significant cancers entirely.

[figure not shown]

Figure 1. Whole-mount pathology slide

usefulness in surgical guidance.

Hundreds of thousands of men could have peace of mind and improved outcomes, if new imaging could accurately detect extra-prostatic extension of prostate cancer to better guide treatment. Recent studies on treatment-related regret in prostate cancer show key drivers of regret are: nerve related injury (erectile dysfunction), loss of masculinity, and positive surgical margins (van Stan, et al. 2020, Baunake, et al. 2020). Cellulyarly targeted molecular imaging (PSMA-PET) appears to have the needed ability to detect aggressive prostate cancer, but requires further testing to validate its

INNOVATION

We currently use multiparametric 3-T MRI (mpMRI), in addition to ultrasound biopsies, to guide surgical therapy, but significant uncertainty remains due to limited sensitivity. Incorporating MRI-guidance does increase the detection of clinically significant prostate cancer compared to systematic biopsy alone (Hu, et al. 2014, Pokorny, et al. 2017, Wysock, et al. 2014). However, recent studies mapping MRI lesions to final whole-mount pathology show significant limitations remain with this imaging approach. For example, a recent study showed only 80% of index (largest) tumors were seen by MRI, and even fewer secondary lesions (Le, et al. 2014). Another recent study showed MRI missed a clinically significant lesion in 26% of patients using whole-mount analysis (Borofsky, et al. 2017). Fittingly, Borofsky titled their paper, *“What are we missing? False negative cancers at Multiparametric MR imaging of the prostate.”* MRI interpretation has also been shown to vary substantially between radiologists, which persisted after correcting for radiologist practice volume (Son, et al. 2017, Son, et al. 2020).

We have performed thousands of prostatectomies at Indiana University and note that many patients have *“prostate confined”* cancer that could have been cured with nerve sparing treatment. The converse is also concerningly true: many patients have positive surgical margins where nerve sparing surgery was performed at sites of extra-prostate extension leaving cancer behind. We were early investigators of PSMA-PET imaging, and since 2017 have been observing whether PSMA-PET could aid in surgical resection. **Using a molecular targeted agent such as ^{68}Ga -PSMA-11 to guide resection represents a significant innovation in surgical planning, appearing to offer better individualization of the treatment plan with reduced surgical margins, when appropriate, and consequently improving quality of life.**

Preliminary Studies

PSMA PET imaging in primary prostate cancer has been reported primarily out of Germany and Australia with few prospective studies in the United States. Few studies utilize the labor-intensive whole-mount pathology as the “gold standard” for rigorous disease characterization, and few studies have comprehensively looked specifically at extra-prostatic extension and surgical resection guidance. Furthermore, the published studies have focused on a small percentage of aggressive prostate cancer (high-risk disease) rather than the majority of pre-metastatic cancers (intermediate risk disease). For example, the only study reported out of the United States was a retrospective

review of 32 higher risk aggressive cancers ($\geq 4+3$) removed by prostatectomy, which found PSMA PET-MRI to be superior to mpMRI (Sensitivity 74% vs 50%, $p<0.001$, Hicks, et al. 2018). A retrospective trial out of Australia compared ^{68}Ga -PSMA-11 PET-CT and mpMRI using a per lesion approach (Berger, et al. 2018). They found index lesion localization was better for PSMA-PET than MRI (100% vs 94%). Secondary lesion sensitivity was much higher for PSMA-PET than for MRI (94% vs 52%). *We need larger prospective studies focused on improved surgical guidance in the patient population posing the greatest challenge in urologic decision-making, patients with intermediate risk disease.*

Preliminary Studies/Data

^{68}Ga -PSMA-11 PET for Early Metastatic Disease. The project investigators have significant experience in PET imaging with ^{68}Ga -PSMA-11. Our initial human experience with ^{68}Ga -PSMA-11 PET was for dosimetry assessment, studying ten prostate cancer patients with biochemical recurrence who had been previously clinically imaged with ^{11}C -acetate under an Expanded Access IND (Green, et al. 2017). The expected utility of ^{68}Ga -PSMA-11 PET was apparent even in that limited series, with ^{68}Ga detecting sites of metastasis not seen in ^{11}C -acetate imaging. We have subsequently dropped ^{11}C -acetate imaging in prostate cancer patients with biochemical recurrence in favor of ^{68}Ga -PSMA-11 PET, and have performed clinical imaging on over 400 patients under Expanded Access IND 131,806.

^{68}Ga -PSMA-11 PET for Diagnosis and Surgical Planning. We recently published an observational trial evaluating ^{68}Ga -PSMA-11 PET-CT or PET-MRI preoperatively in 15 patients with biopsy-proven *high or intermediate-risk* prostate cancer (Bahler, et al. 2019). The PSMA-PET exam was obtained prior to scheduled surgical resection for correlation of imaging findings with whole-mount pathology. All staging ^{68}Ga -PSMA-11 PET/CT scans (15/15) showed suspicious prostate lesions (index lesion) with median (IQR) SUV of 10.0 (6-13); benign prostate had a median (IQR) SUV_{max} of 2.2 (2-3). Good registration was seen between PSMA-PET and whole mount imaging for lethal cancer. For secondary lesions, 8/11 (82%) were detected with ^{68}Ga -PSMA-11 PET; the three missed lesions were of $\leq 10\%$ Pattern 4 ($> 90\%$ pattern 3). Our study was published with the following Editorial Comment: *"This study is...one of the few that has done so for intermediate risk disease and it delineates the accuracy of PSMA imaging to differentiate histological grade groups 1- 3. Prospective well-designed trials validating PSMA imaging in these low prevalence populations are critical and a logical next step based on these study results"* (Emmett and Hofman, 2020).

Figure 2. A lesion at the base of the prostate is seen (30% pattern 4) with ^{68}Ga -PSMA-11 PET-CT scanner.

^{68}Ga -PSMA-11 PET for predicting extra-prostatic extension. Currently, we have 33 prostatectomy cases (each case has right and left nerve bundle) available with preoperative PSMA-PET imaging. Extra-prostatic extension was noted in 26/66 (39%) nerve bundles, and this was predicted in 24/26 (92%) of the cases on PSMA-PET. The PSMA-PET would have changed the treatment plan in 18/33 (55%) of cases, including choosing to spare 12 nerve bundles, while also avoiding nerve sparing in 4 cases of extra-prostatic extension. See **Appendix A** for example PSMA-PET surgeon's report to guide resection.

Prostatectomy carries significant risk for post-treatment urinary and erectile dysfunction. PSMA-PET imaging offers the potential of both cancer control and excellent quality of life for patients whose disease is localized to the prostate. There is an immediate clinical need for validation of advanced imaging (PSMA-PET) in the context of enabling more precise surgical guidance.

3.2 Rationale

Our long-term goal is to improve cancer outcomes and quality of life for prostate cancer patients by bringing novel imaging agents and systems to the diagnosis and treatment of prostate cancer. Prostatectomy carries significant risk for post-treatment urinary and erectile dysfunction. PSMA-PET imaging offers the potential of both cancer control and excellent quality of life for patients whose disease is localized to the prostate (see figure below). There is an immediate clinical need for validation of advanced imaging (PSMA-PET) in the context of enabling more precise surgical guidance.

[figure not shown]

Figure 4. The prostate is located near several anatomic structures important for genitourinary function. Advanced imaging is important to avoid unnecessary treatment of surrounding structures, while ensuring all malignant lesions are treated. We aim to improve quality of life by appropriately avoiding injury to structures 1-4 shown at left. EPE = extra-prostatic extension.

4 STUDY OBJECTIVES

4.1 Primary

1) Evaluate PSMA-PET imaging preoperatively and calculate performance for predicting extra-prostatic extension based on the whole-mount pathology gold standard.

4.2 Secondary

1) Quantify the frequency of proper treatment changes directed by PSMA-PET

2) Compare PSMA-PET performance for predicting extra-prostatic extension to standard-of-care assessments.

Exploratory Endpoints:

3) Assess quality of life changes from preoperative baseline:

IEF-15 (Erectile function score),

EPIC-26 (Pad use),

SF-36 (Overall mental and physical health domains)

4) To assess whether kinetic modeling tools are useful for improving detection of the location and extent of tumor in ^{68}Ga -PSMA-11 PET/CT images. (Going beyond the standard PET map of regional radiotracer concentrations, to additionally examine differences in regional pharmacokinetics in order to possibly better differentiate benign and neoplastic tissue.)

5 CRITERIA FOR EVALUATION

5.1 Primary

1) Sensitivity and Specificity of PSMA-PET imaging for detecting extra-prostatic extension of cancer at the nerve bundles

5.2 Secondary

1) Rate of treatment changes and rate of treatment changes that were appropriate based on pathology.

Exploratory Endpoints

- 2) Sensitivity/ Specificity/ PPV/ NPV for PSMA-PET vs. MRI vs. ultrasound-based nomogram.
- 3) IIEF-15 (Erectile function score), EPIC-26 (Pad use), SF-36 (overall mental and physical health domains).
- 4) Qualitative and quantitative evaluation of changes in PET image appearance after voxel-by-voxel application of kinetic modeling tools to define regional pharmacokinetics (compared to standard PET reconstructions showing simply the integrated concentration of regional radioactivity over the imaging period).

6 ELIGIBILITY CRITERIA

6.1 Inclusion Criteria

To be considered eligible to participate in this study, a patient must meet all the inclusion criteria listed below:

1. Men diagnosed with clinically significant prostate cancer and are scheduling prostatectomy.
2. Prostate pathology results consistent with:
 - a. Gleason 3+4 ≥1 core with pattern 4 ≥20% or
 - b. ≥ 3 cores of Gleason 3+4 or
 - c. NCCN unfavorable intermediate risk or
 - d. NCCN high-risk or
 - e. NCCN very-high risk
3. Scheduled for standard of care MRI or has recently completed standard of care MRI (within 6 months). Willing and able to lie still for approximately 50 minutes in an enclosed space for the MRI.

6.2 Exclusion Criteria

1. Participation in another investigational trial involving research exposure to ionizing radiation concurrently or within 30 days.
2. Does not meet safety criteria for MRI scan (e.g. metal implant that is not allowed, since this is required for comparison).
3. Significant acute or chronic medical, neurologic, or illness in the subject that, in the judgment of the Principal Investigator, could compromise subject safety, limit the ability to complete the study, and/or compromise the objectives of the study.

7 PATIENT REGISTRATION

Patient enrollment will take place over 12 months at a single institution – Indiana University Simon Cancer Center (IUSCC) encompassing Indiana University Hospital (IUH), IU Health North, IU Health North medical office building, IU Health Methodist Hospital and IU Health Neuroscience Center/Goodman Hall, and IU Health Schwarz Cancer Center. Potential patients will be identified in the Urology clinic, or by physician referrals, mostly likely but not exclusively during pre-operative consultations for surgical removal of prostate cancer. All study procedures will take place at IUSCC/IUH/IU-Health Methodist Hospital, with the research imaging performed at the IU Health Goodman Hall outpatient facility or R2 research facility within the Indiana University Department of Radiology and Imagining Sciences. All patients will be registered with the Indiana University (IU) Department of Urology. Regulatory files will be maintained by the Department of Urology. Applicable regulatory documents must be completed and on file prior to registration of any patients. Patients who appear to be eligible for this trial will undergo the Informed Consent Process and be screened for eligibility utilizing the Eligibility Criteria. Individual patient registration will be done in the REDCap database. The original signed Institutional Review Board (IRB) approved Informed Consent Document and completed eligibility checklist will be stored in the following location: Indiana University Department of Urology, [name].

8 STUDY PROCEDURES

8.1 Summary

This patient population will have clinically significant prostate cancer and either already be scheduled for, or in the process of scheduling a prostatectomy. Patients will either have recently had (within 6-months) a standard of care prostate MRI as part of routine care for their prostate cancer. Following the informed consent process, patients who enroll in the study will receive a ^{68}Ga -PSMA-11 PET-CT. The sensitivity and specificity for lesion characterization will be evaluated, along with the ability of the tracer to inform the treatment planning. After patients undergo surgical removal of the prostate it will have a slice-by-slice whole mount analysis to assess the sensitivity and specificity the PSMA PET.

8.2 Study Calendar

	Screening/ Baseline (-90 days)	Imaging (Day 1)	Surgery (Day 2- 45)	1 ⁶ month F/U	3 ⁶ Month F/U	6 ⁶ month F/U	1 ⁶ year F/U
REQUIRED ASSESSMENTS							
Informed Consent	X						
Inclusion/Exclusion	X						
Medical History ¹	X						
Quality of life Assessments ²	X			X	X	X	X
Surgeon plan (pre-PET)	X						
PSMA dose and PET scan		X					
SOC MRI ³		X					
Surgeon plan (post-PET) ⁴		X					
SOC prostatectomy			X				
Surgery plan (performed)			X				
Pathologic assessment of whole mount ⁵			X				

Footnotes:

1. Medical history may be obtained via medical records, as necessary.
2. Quality of Life Assessments include the following:
 - a. IIEF-15 Score (Erectile function)
 - b. EPIC-26 Questionnaire (Urinary function)
 - c. SF-36 Quality-of-life assessment
3. If the patient does not already have a recent SOC MRI (within 6 months), it will need to be completed as per SOC prior to the PSMA-PET scan.
4. This should be completed within 9 days of the scan.
5. The pathologic whole mount assessments may be batch completed per pathology discretion
6. 1-month follow-up is 4-6 weeks. 3-month follow-up is +/-1-month, 6-month and 12-month follow-up are +/-2-months

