Alternatively, we will also assess characterization of the input function will be generated by placing a 3D volume of interest over the abdominal aorta (possibly including the bifurcation) to capture the needed measures of blood pool radioactivity.

- The PET read will be done by a board-certified nuclear medicine specialist (e.g. [name] or similar) and the MRI read will be done by a board certified MR radiologist (e.g. [name] or similar). Suspicious lesions will be marked in a blinded fashion.
- AE assessment: AEs will be assessed at the time of ⁶⁸Ga-PSMA-11 administration any event **not expected** is collected including but not limited to: rash and shortness of breath.
- Safety monitoring following radiopharmaceutical administration will consist of visual and verbal monitoring of the patient after injection, and during and at the conclusion of the PET/CT procedure, with any apparent patient abnormalities, reactions or reported effects noted in the study records.
- The nuclear medicine technologists administering the radiopharmaceutical are responsible for immediately reporting any adverse or unexpected events to the principal investigator or clinical designee, who will report the occurrence of any adverse events to the IRB.
- As in most clinical nuclear medicine procedures, these radiopharmaceuticals are administered at a sub-pharmacologic doses. Adverse events are exceedingly unlikely, as ⁶⁸Ga-HBED-CC has been clinically employed, extensively and without reported incident, in clinical patient diagnostic imaging studies in prostate cancer patients in Germany and other European countries, as well as in over 400 patients locally.

- If there is a discrepancy between the PSMA and conventional MRI scan, the investigators will discuss the treatment plan with the patient at the investigator's discretion. This will be completed through a pre-surgery clinic or virtual visit within 9days of the PET/CT scan.

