8.3.3 Surgery and Pathology

- The standard of care surgical procedure is performed as indicated by the cancer.
- Pathologic assessment: whole mount sections of prostate tissue and routine sections of lymph nodes if applicable will be fixed and analyzed by licensed pathologist per routine care. This typically happens within 2 weeks of prostatectomy.
- Additional study-related pathologic assessment: intraprostatic lesion-based assessment will be done to document the % Gleason pattern 3, 4, and 5 within each lesion. The Extra-prostatic extension and positive margins will be documented. This may be “batched” at the discretion of the pathology department.
- How the knowledge of the PSMA-PET informs treatment will be tracked. Examples of informing the decision include the number and location of ⁶⁸Ga-PSMA-PET detected: additional intraprostatic cancer lesions diagnosed, extra-prostatic extension, seminal vesicle invasion, and lymph node invasion.

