10.6 Analysis of Secondary Objectives

The frequency of proper treatment changes directed by PSMA-PET compared to MRI will be summarized along 95% CI for all evaluable subjects, and separated for 3 areas important for genito-urinary function including: 1) Bladder neck, 2) Nerve bundles, 3) Urethral Sphincter (Figure 4). We will use the McNemar test to compare the sensitivity and specificity values between PET and MRI although data from this pilot study is considered hypothesis generating only due to the small sample size.

The quality of life data including IIEF-15 (Erectile function score), EPIC-26 (Pad use), SF-36 (overall mental and physical health domains) are longitudinal data, which will be analyzed separately. The analysis will start with the graphical representation of the data, where

mean and the standard of mean at each time point will be plotted and linked over time. An exploratory statistical modelling approach will be conducted to analyze the change over time. In particular, a mixed effects model will be used to analyze the data.

The parametric kinetic modeling data will be assessed for goodness-of-fit of the measured regional tissue time-activity curves to the applied kinetic model. Additionally, the images derived by voxel-wise kinetic modeling will be visually compared to standard reconstructions of the integrated regional concentration of radioactivity, assessing apparent lesion size, lesion position, and lesion/background contrast.

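### The pre-PET surgeon plan may be written before the MRI, and in any such patient the rate of PET-directed changes mixes MRI and PET effects

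*Combined protocol and SAP*

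**What the plan says.** - **Calendar, section 8.2.** The row beginning "Surgeon plan (pre-PET" is marked only under Screening/Baseline (-90 days). The MRI row is marked only under Imaging (Day 1). If there is no MRI from the last 6 months, footnote 3 states that "it will need to be completed as per SOC prior to the PSMA-PET scan". The post-PET plan is due within 9 days of the scan.
- **Eligibility, section 6.1, criterion 3.** It begins "Scheduled for standard of care MRI or has recently completed standard of care MRI (within 6 months". A patient whose MRI is still pending can therefore be enrolled.
- **Comparator.** The synopsis says of PSMA-PET: "This will be compared to the standard of care MRI".
- **Analysis, section 10.6.** "The frequency of proper treatment changes directed by PSMA-PET compared to MRI will be summarized", with a 95% CI, overall and for three anatomical areas.
- **Passages bearing on attribution.** Section 8.3.3: "How the knowledge of the PSMA-PET informs treatment will be tracked". Section 8.3.2: "If there is a discrepancy between the PSMA and conventional MRI scan, the investigators will discuss the treatment plan with the patient". Whether this discussion takes place is left to the investigator.

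**The concern.** For the change rate to measure what PET adds to MRI, the first plan must already use the MRI, so that PET is the only new information between the two plans. The protocol fixes the first plan's position relative to PET but not relative to MRI. Where the MRI arrives after the first plan, a change prompted by MRI alone can be credited to PET. The opposite error is also possible: PET may reverse a change that MRI would have caused, so that the two recorded plans agree and a real PET effect is hidden.

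The treatment-change rate is the only endpoint that section 5.2 lists ahead of its exploratory heading. If no MRI-informed plan is recorded before the PET result is known, it cannot be reconstructed later without hindsight.

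**Working it through.** **Order of events.** The text imposes these constraints:

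1. The pre-PET plan precedes PET (its label and its screening column).
2. A missing MRI precedes PET (footnote 3).
3. The post-PET plan follows PET (footnote 4).

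None of them orders the pre-PET plan and the MRI. MRI, plan, PET, plan complies, and so does plan, MRI, PET, plan. The calendar has three plan records (pre-PET, post-PET, performed), and none is defined as after MRI and before PET. Section 8.3.1, which describes screening, does not mention the surgeon plan.

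**Possible size.** The documents state no expected change rate for this trial, so there is no planned figure to reproduce. The nearest is the preliminary rate in section 3.1, 18/33 = 54.5%, stated as 55%.

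Inputs:
- q = 0.55, the share of plans PET would change (preliminary data, used for illustration).
- f, the share of patients whose first plan precedes the MRI. Not given; assumed 0 to 0.5.
- m, the share of those plans that MRI alone would change. Not given; assumed 0 to 0.4.
- r, the chance that PET reverses an MRI-driven change when both act. Not given; 0 to 1.
- MRI-driven and PET-driven changes are assumed independent.

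In a patient with a late MRI, the recorded plans differ if PET alone acts, if MRI alone acts, or if both act without reversal:

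(1 - m)q + m(1 - q) + mq(1 - r) = q + m(1 - q - qr)

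The bias in the overall rate is therefore f × m × (1 - q - qr).

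At the upper limits, f × m = 0.5 × 0.4 = 0.20:

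| r | Bias | Patients out of 50 |
|---|---|---|
| 0 | 0.20 × 0.45 = +0.090 | +4.5 |
| 0.5 | 0.20 × 0.175 = +0.035 | +1.75 |
| 1 | 0.20 × (-0.10) = -0.020 | -1.0 |

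- With f = m = 0.1, the bias runs from 0.01 × (-0.10) = -0.001 to 0.01 × 0.45 = +0.0045.
- With f = 0 it is zero.
- The sign turns negative when r exceeds (1 - q)/q = 0.45/0.55 = 0.82.

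**Sensitivity to q.** The exact 95% CI of 18/33 is 0.364 to 0.719. With f × m = 0.20, q = 0.364 and r = 0 give 0.20 × 0.636 = +0.127; q = 0.719 and r = 1 give 0.20 × (-0.438) = -0.088.

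**Against sampling error.** For a rate of 55% in 50 patients, the 95% half-width is 1.96 × sqrt(0.55 × 0.45/50) = 0.138, or 0.148 after adding the continuity correction 1/(2 × 50) = 0.010. The biases above are smaller than this, but only because f was capped at 0.5. With f = 1, m = 0.4 and r = 0, the bias is 0.4 × 0.45 = +0.18, which exceeds it.

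**The case against.** The strongest reply is that the wrong order is permitted but unlikely.

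- Section 3.1 describes MRI as a current input to surgical planning at this institution, so a plan written without it would depart from usual practice.
- Section 6.2 excludes patients who cannot have an MRI, because the comparison needs one.
- Section 8.1 describes patients with a recent routine MRI.
- Section 7 expects to identify patients "mostly likely but not exclusively during pre-operative consultations for surgical removal of prostate cancer".
- The calendar columns are weak evidence of sequence. Screening can run up to the scan, and the Day 1 mark for MRI is not literal, since footnote 3 allows it earlier.
- The labels pre-PET and post-PET suggest two plans meant to differ only by PET.

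All of this stands as evidence of intent and as a reason to expect few affected patients. It does not set the order. The sentence in 8.1 is visibly incomplete and does not override criterion 3 or footnote 3. Tracking how PET informs treatment, and discussing PET-MRI discrepancies, do not supply a rule for attributing a change when the MRI is also new since the first plan.

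The reply is also right that f, m and r are assumptions. Independence is doubtful too, because both scans image the same disease. The figures illustrate a mechanism and are not bounds. Finally, section 10.6 calls the pilot data hypothesis generating, which limits the consequences.

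**Conclusion.** The concern holds in its conditional form: the protocol allows the pre-PET plan to precede the MRI, and in any patient where it does, the endpoint does not isolate PET. It does not force that order. The number affected is unknown and may be zero, and the direction of the bias is undetermined. Under the stated assumptions the bias at q = 55% runs from -2.0 to +9.0 points, or from -8.8 to +12.7 points if q varies over its exact CI. A larger affected share would widen both ranges.

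Being smaller than the CI half-width does not make the bias harmless, because the interval neither includes it nor would reveal it. Bias in the rate of appropriate changes, and by anatomical area, was not computed. Sensitivity, specificity and the sample size are unaffected. The change should be made, since it is cheap and the missing record cannot be recovered afterwards.

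**What to change.** 1. In section 8.2, add a footnote requiring the pre-PET plan to be recorded, or re-recorded, after the MRI read is available and before the PET result is disclosed to the surgeon. Record the date of each plan alongside the dates of the MRI read and the PET disclosure.
2. In section 10.6, define a PET-directed change as a difference between the post-PET plan and this MRI-informed pre-PET plan. Report separately any pair of plans recorded out of order.

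The cost is one footnote, the date entries on the form and one or two sentences in 10.6, with no extra visit or procedure. For some patients the surgeon completes the form later, or twice. If no patient is affected, the dates will show it.
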